10.2. PRIOR, CONCOMITANT, AND RESCUE MEDICATIONS AND THERAPIES

All medications recorded on the Concomitant Medications CRF page will be coded using the World Health Organization Drug Dictionary Enhanced (WHO-DDE), September 2016 version. Medications will be listed and summarized by Anatomical Therapeutic Chemical (ATC) Level 1 and Preferred Name. The highest ATC drug level available in the data will be presented, starting with ATC level 4 drug class. Level 3 will be presented if level 4 is missing, and level 2 will be presented if both level 3 and level 4 are missing. All prior and concomitant medications, all rescue medications, and epinephrine medications will be listed separately.

Prior medications are defined as those which are only taken prior to the date of the first dose of study product on Day 1 (i.e., medication end date is prior to the date of first dose of study product). For Group 2, prior medications are those prior medications entered on the concomitant medications page of ARC003. For Group 1, prior medications are those prior medications entered on the concomitant medications page of ARC004.

Concomitant medications are medications taken at any time during the ARC004 treatment period. Any medications recorded for which dosing began after the last dose of study treatment will also be classified as concomitant medications. As needed (PRN) medications, which may or may not be taken for long periods of time, but which are prescribed to the subject for a period that overlaps with the active treatment period, will be considered concomitant medications. If it cannot be determined whether a medication was received prior to the start of study product dosing due to partial or missing medication start and/or end dates, it will be considered a concomitant medication.

Rescue medications are any medication used to treat symptoms of an acute allergic reaction. Unless administered during a DBPCFC, each use of a rescue medication during OIT should be associated with a corresponding adverse event (AE).

Prior medications and concomitant medications excluding rescue medications will be summarized by ATC Class, Preferred Name and group/cohort. Subjects will be counted no more than one time per Preferred Name and no more than one time per ATC Level 4 in the summary.

Rescue medications will be summarized by ATC Class and Preferred Name for the following group/cohort periods:

- Group 1: IDE and up-dosing, Maintenance, and Overall

Sponsor: Aimmune Therapeutics, Inc.

Protocol: ARC0004

Version: Version 1.0, 10Jul2019

- Group 2 Cohort 2: QOD, BIW, and Overall
- Group 2 Cohort 1 (includes QD only)
- Group 2 Cohort 3A (includes QD only)
- Group 2 Combined Cohorts 3 B and C: QD, QOD, BIW, and Overall
- Group 2 Overall QD
- Group 1, Group 2 Cohort 1, Group 2 Cohort 2, Group 2 Cohort 3A, Group 2 Cohort 3B, and Group 2 Cohort 3C by Maintenance and Exit DBPCFC

Concomitant non-drug therapies will be listed by subject.

Sponsor: Aimmune Therapeutics, Inc.

Protocol: ARC0004

Version: Version 1.0, 10Jul2019

10.3. ADVERSE EVENTS

Treatment-emergent adverse events (TEAEs) will be summarized excluding symptoms recorded during the food challenges. The AE summaries will report AEs and in-clinic dosing symptoms.

If symptoms are recorded as part of an anaphylactic reaction, only the single anaphylactic reaction event will be summarized and not the individual symptoms.

All reported adverse events (AEs) will be classified into System Organ Class (SOC) and Preferred Term (PT) using Medical Dictionary for Regulatory Activities (MedDRA) version 19.1. The 5-point CoFAR severity grading scale was used for coding allergic reactions. The 3-point Muraro grading scale was used for grading the severity of anaphylactic reactions. The 5-point CTCAE severity grading scale was used for coding all other adverse events.

In Group 1, treatment-emergent adverse events are defined as those AEs with onset after the first dose of study product in ARC004 and no more than 30 days after the last dose of study product. In Group 2, as all patients are assumed to be continuing AR101 from study ARC003, all reported adverse events with onset no more than 30 days after the last dose of study product will be defined as treatment-emergent. Non treatment-emergent AEs will be included in subject listings, but not summarized. An additional summary of age group 18-55 will be included for the safety population for the overall AE summary and SAE summary.

Summaries that are displayed by system organ class and preferred terms will be ordered by descending incidence of system organ class and preferred term within each system organ class. Summaries displayed by preferred term only will be ordered by descending incidence of preferred term. Summaries of the following types will be presented:

- Overall summary of number of unique TEAEs and treatment-emergent serious adverse events (TESAEs), subject incidence of TEAEs and TESAEs meeting various criteria and exposure-adjusted incidence rates of TEAEs and TESAEs meeting various criteria, where exposure incidence rates are defined as the total number of events divided by the total number of subject-years at risk during the study period;
- Subject incidence of TEAEs by MedDRA system organ class and preferred term;
- Exposure-adjusted event rates for the most frequent TEAEs (i.e., TEAEs occurring in $\geq 5\%$ of the Safety Population) by MedDRA preferred term;

Sponsor: Aimmune Therapeutics, Inc.

Protocol: ARC0004

Version: Version 1.0, 10Jul2019

- Subject incidence of treatment-related AEs by MedDRA system organ class, and preferred term;
- Exposure-adjusted event rates for the most frequent treatment-related AEs (i.e., treatment-related AEs occurring in $\geq 5\%$ of the Safety Population) by MedDRA preferred term;
- Subject incidence of grade ≥ 3 severity TEAEs by MedDRA system organ class and preferred term;
- Subject incidence of grade ≥ 3 severity treatment-related AEs by MedDRA system organ class and preferred term;
- Subject incidence of TESAEs by MedDRA system organ class and preferred term;
- Subject incidence of TEAEs leading to discontinuation of study product by MedDRA system organ class and preferred term;
- Subject incidence of TEAEs associated with Epinephrine use by MedDRA system organ class and preferred term.
- Subject incidence of hypersensitivity TEAEs by MedDRA system organ class and preferred term, where hypersensitivity TEAEs are all TEAEs from the in-clinic dosing CRFs and all TEAEs indicated as an allergic reaction on the AE CRF
- Subject incidence of hypersensitivity treatment-related AEs by MedDRA system organ class and preferred term;
- Exposure-adjusted event rates for the most frequent hypersensitivity TEAEs (i.e., hypersensitivity TEAEs occurring in $\geq 5\%$ of the Safety Population) by MedDRA preferred term;
- Subject incidence of TEAEs associated with nonstudy product food allergen exposure by MedDRA system organ class and preferred term; and
- Subject incidence of TEAEs leading to early withdrawal by MedDRA system organ class and preferred term

At each level of summarization (e.g., any AE, system organ class, and preferred term), subjects experiencing more than one TEAE will be counted only once within each study period. In the summary of TEAEs by severity grade, subjects will be counted once at the highest severity reported at each level of summarization.

Sponsor: Aimmune Therapeutics, Inc.

Protocol: ARC0004

Version: Version 1.0, 10Jul2019

Adverse event data will be presented in data listings by age group (4-17 years and 18-55 years), group/cohort, subject, study period, and event. Serious TEAEs; Serious DBPCFC AEs; severe, life-threatening, or fatal adverse events; anaphylactic reactions; and AEs leading to discontinuation, reduction, or interruption of the study product will be presented in separate data listings.

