7.1 Definitions

All safety events observed under this protocol are reported through the electronic data capture (EDC) system for the duration of the study. Some safety events arising under certain defined conditions are recorded on specific forms as follows.

- Any allergic symptoms observed during in-clinic dosing will be recorded directly on the Escalation/In-Clinic Dosing Form (also referred to as a Study Product Administration Form), and are not recorded on an AE form (to avoid duplicate reporting) unless the event is considered an SAE. These symptoms are, however, by definition, AEs ([Section 7.2](#)) and will be reported as such in the database.
- Non-serious AEIs are reported on an AEI form and include anaphylaxis episodes meeting the criteria below, accidental food allergen exposures, GI AEs resulting in prolonged disruption of dosing, AEs associated with the use of epinephrine, and severe AEs ([Section 7.3.3](#)). They are not to be reported on an AE form (to avoid duplicate reporting) unless the event is considered an SAE, as defined below ([Section 7.3.2](#)).
- If any safety event meets the definition of an SAE (whether or not related to dosing), it will also be recorded on an AE/SAE form.
- Skin prick test reactions are not considered AEs unless the reaction, or a complication from the procedure, is considered an SAE, as defined below ([Section 7.3.2](#)).
- Food challenge reactions that occur in the clinic are captured on study specific forms and are not reported on an AE form (to avoid duplicate reporting) unless the event is considered an SAE, as defined below ([Section 7.3.2](#)).
 - As study product is not used in the DBPCFCs, no AEs occurring from Screening DBPCFC can be treatment-related (referring to treatment with study product).
 - For food challenge reactions that occur at the Exit DBPCFC, it will also usually be the case that study product was not the cause of the reaction, as study product is not used in the challenge. There is, however, the possibility that dosing with study product in the days prior to Exit DBPCFC could contribute to a reaction encountered during the challenge. The investigator must determine if dosing with study product in the days prior to Exit DBPCFC likely contributed to any observed reaction. If so, the investigator should indicate the level of the relatedness, and provide a brief explanation as to the manner in which prior dosing with study product was thought to be contributory.

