9.2 Study Endpoints

9.2.1 Primary Endpoint

The primary endpoint is the frequency of treatment-related AEs, including SAEs, during the overall study period (from enrollment to the end of EM).

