3. ENDPOINTS

3.1. PRIMARY ENDPOINT

The primary endpoint is the frequency of treatment-related AEs, including SAEs, during the overall study period (from enrollment to discontinuation/exit). ARC004 is specifically designed to begin exploring alternate (eg, nondaily) oral immunotherapy (OIT) extended maintenance dosing regimens. The data generated for alternative dosing regimens in ARC004 are expected to be exploratory and hypothesis-generating.

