10.6. SYMPTOMS DURING DBPCFC

During each food challenge, the severity of pre-specified symptoms is rated on the CoFAR scale as mild, moderate, severe, life-threatening, or death at each dose level of each food product. In addition, the presence of any dose related symptoms is identified.

The number of subjects experiencing any dose related symptoms and the maximum severity of any symptoms will be summarized by individual dose level and overall during the Screening peanut challenge, Maintenance peanut challenge (Group 1 only) and the Exit peanut challenge by group/cohort. Subjects will be counted at most once per type of challenge and dose level for symptom severity at the most severe level recorded for that subject.

Symptoms at the maintenance and Exit DBPCFCs will be listed by age group, group/cohort, and subject.

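### SAP 10.3 leaves food-challenge symptoms out of every TEAE summary even when judged AR101-related, although SAP 3.1 runs the primary endpoint of treatment-related AEs to exit

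*SAP*

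**What the plan says.** **Relatedness.** Protocol 7.1 notes that challenges do not use study product, so it will usually not be the cause of an Exit challenge reaction. It nevertheless allows that recent dosing may have contributed: "The investigator must determine if dosing with study product in the days prior to Exit DBPCFC likely contributed to any observed reaction". It continues: "If so, the investigator should indicate the level of the relatedness", with a short explanation.

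**Data capture.** In the same section: "Food challenge reactions that occur in the clinic are captured on study specific forms and are not reported on an AE form", unless the event is serious. Challenge SAEs go on the AE/SAE form set as well as the challenge form.

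**Primary endpoint.** SAP 3.1: "The primary endpoint is the frequency of treatment-related AEs, including SAEs, during the overall study period (from enrollment to discontinuation/exit". Protocol 9.2.1 closes the window earlier: "The primary endpoint is the frequency of treatment-related AEs, including SAEs, during the overall study period (from enrollment to the end of EM".

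**Analysis.** SAP 10.3: "Treatment-emergent adverse events (TEAEs) will be summarized excluding symptoms recorded during the food challenges". The sentence that follows says the AE summaries cover AEs and in-clinic dosing symptoms. Among the planned listings are "Serious TEAEs; Serious DBPCFC AEs; severe, life-threatening, or fatal adverse events; anaphylactic reactions". SAP 10.6 handles challenge symptoms separately: "the maximum severity of any symptoms will be summarized by individual dose level and overall". SAP 11, which lists departures from the protocol, mentions neither the exclusion nor the changed window.

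**The concern.** Safety is the primary endpoint of this trial, and it is defined by relatedness to AR101. The protocol makes sites record a causality judgement for reactions at the Exit challenge. The SAP then sets an endpoint window that reaches exit, but removes challenge symptoms from the AE tables without looking at that judgement. The result is a causality assessment that no planned table uses, and a counting rule at odds with the SAP's own endpoint definition. For related challenge SAEs the wording is loose enough that two programmers could count the same event differently in the primary endpoint.

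**Working it through.** **The plan's own safety figure.** SAP 2.4 and Protocol 9.4 give an 80% probability of seeing at least one AE with about 400 subjects and a background rate of 4 per 1,000. Check: 1 − (1 − 0.004)^400 = 1 − 0.996^400 = 0.799. It reproduces, but says nothing about which events are counted. That has to be settled by reading the sections together.

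**Path of a non-serious Exit reaction judged AR101-related**
1. It is recorded on a challenge form, not an AE form (Protocol 7.1).
2. It normally falls within the treatment-emergent window, which runs to 30 days after the last dose (SAP 10.3).
3. It is removed from the TEAE summaries by SAP 10.3 whatever its relatedness, and it is not an in-clinic dosing symptom, so it does not return by that route.
4. It appears in SAP 9.1.3 and 10.6 by challenge dose and severity, and in SAP 9.1.4 if epinephrine was given. None of these is split by relatedness to AR101. SAP 10.13 does split epinephrine episodes by relatedness, but leaves out food challenges.
5. If it is called anaphylaxis, SAP 10.14 summarises it under Exit DBPCFC columns. That section classes a reaction as related when any of its symptoms is, but relatedness is not among the items it lists for tabulation. Protocol 7.3.3.1 also says challenge symptoms are not to be treated as anaphylaxis events, so use of this route is uncertain.

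Such a reaction therefore reaches no treatment-related table.

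**Path of a related challenge SAE**
1. It is on the AE/SAE form as well as the challenge form, and Protocol 7.5.2 requires a relatedness assessment.
2. SAP 10.3 excludes symptoms recorded during challenges but includes AEs. An SAE on the AE/SAE form could be read as either.
3. The listings name serious TEAEs and serious DBPCFC AEs as separate categories. That suggests challenge SAEs are not TEAEs, but no sentence says so.

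The status is unsettled.

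**Endpoint window.** SAP 7.5 ends Extended Maintenance at the last dose before the Exit DBPCFC and defines the Exit DBPCFC as its own period. Under the protocol's wording the Exit challenge then lies outside the primary endpoint; under SAP 3.1 it lies inside. Group 1's Maintenance DBPCFC comes before Extended Maintenance, so it is inside both windows, and the SAP 10.3 exclusion covers it too. Protocol 7.1's specific instruction names only the Exit challenge, but an SAE at either challenge needs a relatedness assessment.

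**Size.** No rate of AR101-related challenge reactions is given. The following is for scale only:
- If 0.5%, 1% or 2% of 400 subjects had an Exit reaction judged related (assumed rates), then 400 × 0.005 = 2, 400 × 0.01 = 4 or 400 × 0.02 = 8 subjects would be outside the TEAE tables.
- Protocol 1.4.1 anticipates serious life-threatening anaphylactic reactions at under 0.1%, without stating the unit. Taken as a per-subject ceiling for one challenge in 400 subjects (assumption), at most 400 × 0.001 = 0.4 events are expected, with at most a 1 − 0.999^400 = 33% chance of any. This is regardless of cause; related events would be fewer.
- In a related-SAE row, one subject is 1/50 = 2.0 points at the planned size of Cohort 2 and 1/120 = 0.8 points for Cohort 1. The main safety tables cover ages 4 to 17, so actual denominators will differ.

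**The case against.** The best defence is that challenge reactions are provoked on purpose with a product that is not AR101, so separating them from treatment AEs is sensible. The protocol itself keeps non-serious ones off the AE form, and the SAP follows that data flow. Much of this stands: separate reporting is reasonable, and few reactions should be attributed to AR101. It does not fully answer the point. The protocol's stated reason for keeping these reactions off the AE form is to prevent double reporting. In-clinic dosing symptoms are kept off it for the same reason, yet SAP 10.3 brings them into the AE summaries. The protocol does, however, expressly call only the dosing symptoms AEs. Nor does the data flow explain why the required relatedness judgement is used nowhere.

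A reader might infer more than the text supports:
- *That related challenge SAEs never enter the primary endpoint.* The text leaves this open. They are on the AE/SAE form and are at least listed, and SAP 10.14 summarises anaphylaxis at the Exit DBPCFC, including cases that were SAEs.
- *That the primary endpoint is undercounted by definition.* For the Exit challenge this holds only under the SAP's window, not under the protocol's read with SAP 7.5.
- *That the loss is differential, because daily dosers will have dosed more recently before the challenge than twice-weekly dosers.* This is plausible, but no figure in the documents bears on it.
- *That each omitted reaction lowers overall incidence.* Subjects count once per summary level, so one with an earlier related AE adds nothing to the any-treatment-related row.

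**Conclusion.** The point holds in limited form. SAP 10.3 excludes challenge symptoms without exception, and as written this keeps non-serious Exit reactions judged AR101-related out of every treatment-related table, within a window that SAP 3.1 extends to exit. For related challenge SAEs the SAP does not say whether they count, and its separate listing leans towards not counting them. The anaphylaxis summary covers part of the gap but does not tabulate relatedness. The numerical effect cannot be derived from the documents. It is probably small, because Protocol 7.1 expects study product usually not to be the cause; the counts shown for scale rest on assumed rates. The case for acting is that a stated counting rule conflicts with the SAP's own primary endpoint and is cheap to put right, not that a material bias has been shown.

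**What to change.** 1. Amend SAP 10.3 so that challenge reactions and challenge SAEs recorded as related to study product are reported by group and cohort in a separate row (Exit DBPCFC, related to AR101) beside the treatment-related AE and TESAE summaries. Give subject counts only: SAP 7.5 leaves DBPCFC periods out of treatment duration, so an exposure-adjusted rate would have no matching denominator.
2. State that challenge SAEs judged related count in the treatment-related SAE total.
3. Reconcile the primary endpoint window between Protocol 9.2.1 (end of EM) and SAP 3.1 (discontinuation/exit).
4. Declare in SAP 11 any exclusion that is retained.

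The cost is SAP wording and a little programming, using a judgement that the protocol already requires. The case report forms are not part of the documents, so how relatedness is captured on the challenge form needs confirming first. A separate row keeps provoked reactions distinguishable from dosing reactions. The downside is a treatment-related figure that may be slightly higher.

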6.5 Assessment and Treatment of Allergic Reactions to Peanut OIT

6.5.1 Assessment of the Severity of Acute Allergic Reactions to Peanut OIT

Subjects may develop allergic symptoms during the course of OIT, similar to those seen during other desensitization protocols (eg, venom immunotherapy, drug desensitization, desensitization to aeroallergens by subcutaneous injection). The severity of the reaction will

be determined based on the investigator's judgment. The following definitions, developed to be consistent both with the PRACTALL consensus report on DBPCFC, and with the CoFAR grading system for allergic reactions, are provided as a general guide.

Mild Symptoms:

- Skin – limited (few) or localized hives, swelling (eg, mild lip edema), skin flushing (eg, few areas of faint erythema), or mild pruritus (eg, causing occasional scratching)
- Respiratory – rhinorrhea (eg, occasional sniffing or sneezing), nasal congestion, occasional cough, throat discomfort
- Gastrointestinal – mild abdominal discomfort (including mild nausea), minor vomiting (typically a single episode) and/or a single episode of diarrhea

Moderate symptoms:

- Skin – systemic hives (eg, numerous or widespread hives), swelling (eg, significant lip or face edema), pruritus causing protracted scratching, more than a few areas of erythema, or pronounced erythema
- Respiratory – throat tightness without hoarseness, persistent cough, wheezing without dyspnea
- Gastrointestinal – persistent moderate abdominal pain/cramping/nausea, more than a single episode of vomiting and/or diarrhea

Severe symptoms:

- Skin – severe generalized urticaria/angioedema/erythema
- Respiratory – laryngeal edema, throat tightness with hoarseness, wheezing with dyspnea, stridor
- Gastrointestinal – severe abdominal pain/cramping/repetitive vomiting and/or diarrhea
- Neurological – change in mental status
- Circulatory – clinically significant hypotension ([Appendix 3](#))

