7.8.2 Individual Stopping Rules

Individuals may stop the study at any time by withdrawing their consent if they experience subjectively intolerable AEs, dosing symptoms, or for any other reason. Because ARC004 is exploring alternative dosing schedules, the approach to individual stopping rules caused by dose-related AEs varies by regimen. All subjects discontinuing the study early and permanently discontinuing AR101 treatment will return to the CRC for an Early Discontinuation Visit no later than 14 days after the last AR101 exposure.

QD Dosing Regimens

When on QD dosing regimens (including Up-dosing and Maintenance for Group 1, and QD EM for both Groups, as applicable), 7 or more consecutive days of missed daily dosing due to non-compliance constitutes an individual stopping rule. During Up-dosing, Group 1 subjects must halt up-dosing and re-start with a reduced dose if more than 4 days of dosing are missed. Missing 3 or more consecutive days on 3 occasions while on daily dosing in any period is an individual stopping rule, as is missing 15 or more consecutive days of QD dosing for any reason.

QOD, BIW, QW, or QOW Regimens

Any subject receiving nondaily dosing (QOD, BIW, QW, or QOW) who has 1 related SAE; 1 related AE graded severe; 2 related AEs occurring on separate occasions, both graded moderate; or 3 consecutive doses judged “not tolerated” will be considered as a treatment failure and discontinued from ARC004 for safety reasons. Such subjects may be eligible to enroll in ARC008 and receive AR101 daily in the Repeat Up-dosing period. If ARC008 is not available, the subjects will begin daily dosing and have visits in the Repeat Up-dosing period in ARC004. Once the subject reaches the target dose of 300 mg daily and maintains that dose for 2 weeks, that subject will be able to continue this dose regimen until ARC008 is available.

Occurrence of any of the following will result in the cessation of dosing and the subject being discontinued from the study as an escalation failure nonresponder:

- Failure to accomplish up-dosing of study product after 3 attempts
- Failure to identify a tolerated dose of study product after 3 attempts at dose reduction

Finally, administration of 3 or more doses of epinephrine for the treatment of any dose-related allergic reaction in any subject during any period is an individual stopping rule.

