Appendix 3: Criteria for Suspected Diagnosis and Severity Grading of Anaphylaxis

Criteria for Suspected Diagnosis

Anaphylaxis is likely when any 1 of the 3 following sets of criteria is fulfilled:

1. Acute onset of an illness (minutes to hours) with involvement of:
 - Skin/mucosal tissue (eg, *generalized* hives, itch or flush, swollen lips/tongue/uvula) *AND*
 - Airway compromise (eg, dyspnea, stridor, wheeze/ bronchospasm, hypoxia, reduced peak expiratory flow rate [PEFR]) *AND/OR*
 - Reduced blood pressure (BP) or associated symptoms (eg, hypotonia, syncope, incontinence)
2. Two or more of the following that occur rapidly after exposure to the allergen (minutes to hour):
 - Skin/mucosal tissue (eg, *generalized* hives, itch/flush, swollen lips/tongue/uvula)
 - Airway compromise (eg, dyspnea, stridor wheeze/bronchospasm, hypoxia, reduced PEFR)
 - Reduced BP or associated symptoms (eg, hypotonia, syncope, incontinence)
 - *Persistent* gastrointestinal (GI) symptoms (eg, nausea, vomiting, crampy abdominal pain)
3. Reduced BP after exposure to the allergen (min to h):
 - Infants and Children: low systolic BP (age-specific) or > 30% drop in systolic BP*
 - Adults: systolic BP < 90 mmHg or > 30% drop from baseline

* Low systolic BP for children is defined as < 70 mm Hg from 1 month to 1 year; less than (70 mm Hg + [2 × age]) from 1 to 10 years; and < 90 mm Hg from age 11 to 17 years.

Note: Isolated skin or mucosal lesions following the ingestion of a food constitute a “food-induced allergic reaction”.

Table: Criteria for Severity Grading

Staging System of Severity of Anaphylaxis	
Stage	Defined By
1. Mild (skin & subcutaneous tissues, GI, &/or mild respiratory)	Flushing, urticaria, periorbital or facial angioedema; mild dyspnea, wheeze or upper respiratory symptoms; mild abdominal pain and/or emesis
2. Moderate (mild symptoms + features suggesting moderate respiratory, cardiovascular or GI symptoms)	Marked dysphagia, hoarseness and/or stridor; shortness of breath, wheezing & retractions; crampy abdominal pain, recurrent vomiting and/or diarrhea; and/or mild dizziness
3. Severe (hypoxia, hypotension, or neurological compromise)	Cyanosis or SpO ₂ ≤ 92% at any stage, hypotension, confusion, collapse, loss of consciousness; or incontinence

Criteria for diagnosis and for severity grading have been adapted from [Muraro et al, 2007](#), and [Muraro et al, 2014](#).

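### The grade ≥3 AE tables mix CoFAR grades with anaphylaxis stages, so a reaction with stridor or wheezing with dyspnea can drop out once it is called anaphylaxis

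*SAP*

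**What the plan says.** SAP 10.3 uses a different severity scale for each type of event. One sentence covers allergic reactions: "The 5-point CoFAR severity grading scale was used for coding allergic reactions". Anaphylaxis has its own, shorter scale: "The 3-point Muraro grading scale was used for grading the severity of anaphylactic reactions". CTCAE serves for everything else. Protocol 7.4 makes the same split. For the AE summaries the SAP adds: "If symptoms are recorded as part of an anaphylactic reaction, only the single anaphylactic reaction event will be summarized and not the individual symptoms".

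Among the planned tables are the subject incidence of grade ≥3 "severity TEAEs by MedDRA system organ class and preferred term" and of grade ≥3 "severity treatment-related AEs by MedDRA system organ class and preferred term". There is one cutoff for all scales and no crosswalk.

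The protocol's severity lists differ. For allergic reactions, Protocol 6.5.1 places these respiratory signs under severe: "laryngeal edema, throat tightness with hoarseness, wheezing with dyspnea, stridor". Section 7.3.3.4 repeats the list. For anaphylaxis, Appendix 3 puts the following in stage 2, moderate: "Marked dysphagia, hoarseness and/or stridor; shortness of breath, wheezing & retractions". Stage 3 is reserved for hypoxia, hypotension or neurological compromise.

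Protocol 7.8.2 uses severity words in the individual stopping rule for nondaily regimens: "1 related AE graded severe; 2 related AEs occurring on separate occasions, both graded moderate". It does not say which scale they refer to when a reaction is both allergic and anaphylactic.

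**The concern.** A grade ≥3 table is read as the list of the worst events. Here the number 3 comes from two scales with different thresholds. A sign that reaches the top clinical category on one scale sits one category lower on the other, and the reaction moves to the second scale when more organ systems become involved. The more extensive reaction can therefore be left out of the table while the more limited one is counted. Because the component symptoms are removed from the AE summaries, the severe symptom is not counted under its own term either.

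At stake is how a reader interprets the two severity tables for each regimen, in a study whose purpose is to describe safety at longer dosing intervals. The affected rows are the any-event row and the system organ class rows. The preferred-term row for anaphylactic reaction rests on a single scale and is internally consistent.

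**Working it through.** No figure in the plan bears on this point, so there is none to reproduce. The check is a comparison of definitions, followed by a look at whether the effect can be sized.

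**Step 1: the same sign on each scale.**

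| Sign | Protocol 6.5.1 and 7.3.3.4 | CoFAR table (Appendix 4) | Anaphylaxis stage (Appendix 3) |
|---|---|---|---|
| Stridor | Severe | Not named | Stage 2 |
| Wheezing with dyspnea | Severe | Grade 3 (bronchospasm with dyspnea) | Stage 2; stage 1 if the dyspnea is mild |
| Hypoxia, hypotension, neurological compromise | Severe (hypotension, mental status change) | Grade 3 or 4 | Stage 3 |

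**Step 2: which stage counts as grade ≥3.** The SAP does not say. Appendix 3 labels stage 3 severe, and SAP 7.6 treats severe as the highest category of that scale when it imputes missing values. Stage 3 alone is the natural reading.

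**Step 3: apply SAP 10.3 to three reactions.**

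- Stridor or wheezing with dyspnea, not called anaphylaxis: severe, so it is in the tables.
- The same sign in a reaction called anaphylaxis, without stage 3 features: stage 2 (possibly stage 1), symptoms collapsed, so it is not in the tables.
- The same sign in anaphylaxis with stage 3 features: stage 3, so it is in the tables.

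The middle case is out of order.

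**Step 4: does another passage repair it?** SAP 10.14 makes a reaction serious, or related, if any component symptom is, but has no such rule for severity. Protocol 6.5.2 says that a reaction's severity generally follows its worst symptom, which points the other way from the stage-only grade. Protocol 7.3.3.4 does not require a severe AE to be reported separately when it is part of anaphylaxis. Nothing corrects the two tables.

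**Step 5: size.** Let s be the share of subjects with a reaction containing a sign graded severe under 6.5.1 or CoFAR. Let f be the fraction of those subjects whose only such reactions are coded stage 1 or 2 anaphylaxis. The table shows s × (1 − f) and loses s × f. The documents give neither s nor f. The nearest figure is in Protocol 1.4.1, where severe symptoms are expected in under 1% of subjects, based on earlier OIT studies. Taking s = 1% with the planned sizes in 7.8.3:

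- Cohort 2: 50 × 0.01 = 0.5 subject with any severe symptom.
- Cohorts 3B and 3C combined: 175 × 2/3 = 117, × 0.01 = 1.2 subjects.
- All of Group 2: (120 + 50 + 175) × 0.01 = 3.45 subjects.

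With f assumed between 25% and 75%, the loss is 0.25 to 0.75 percentage points. With s assumed at 2%, the tables would show 1.5% down to 0.5%. These values of f, and s = 2%, are assumptions. The 1% figure is only a loose guide for nondaily dosing, because Protocol 1.3 says published peanut OIT studies all dosed daily.

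**The case against.** The best defence is that the plan prespecifies the scale by event type. Protocol 7.4 sends anaphylactic reactions to the EAACI stages, so a stage 2 reaction is reported as what it was graded. That is right, and it is a reason not to overwrite the stage. It does not supply a meaning for grade ≥3 on a 3-stage scale, nor does it make the pooled rows comparable.

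Second, the information is not lost. SAP 10.14 tabulates anaphylaxis by maximum stage, seriousness, epinephrine use and individual symptoms. SAP 10.5 summarizes dosing symptoms by maximum CoFAR severity, and 10.13 shows epinephrine episodes by severity of the associated event. Severe events and anaphylactic reactions have their own listings. This stands, and it confines the problem to two tables.

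Third, the severity lists are guides under investigator judgment, and the CoFAR table does not name stridor. This also stands. Some apparent mismatches are weak. Section 6.5.1 already puts more than one episode of vomiting under moderate, which fits the recurrent vomiting of stage 2. Hoarseness alone is not the throat tightness with hoarseness that 6.5.1 calls severe. The firm overlap is stridor and wheezing with dyspnea.

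Fourth, component CoFAR grades may not always exist. Protocol 7.2 asks for each symptom of an allergic reaction on its own log line, but 7.1 routes non-serious anaphylaxis to a separate form. That limits the remedy to reactions with recorded symptom grades.

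**Conclusion.** The point holds as a reporting defect in the grade ≥3 TEAE and treatment-related AE tables of SAP 10.3. It rests on two assumptions: that only stage 3 meets the cutoff, and that investigators grade broadly as the protocol's lists suggest. If the SAP intended another mapping, its omission is itself the gap. The size cannot be determined from the documents.

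A reader might infer more, and the documents do not support it:

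- **That the primary endpoint is understated.** It is the frequency of treatment-related AEs at any severity. An anaphylactic reaction stays in that count, and any related symptom makes the reaction related.
- **That a cohort's grade ≥3 incidence falls by several percentage points, or that a column empties.** No anaphylaxis rate is given, and a loss of that order sits badly with the under 1% expected for severe symptoms of every kind.
- **That comparisons between regimens are biased.** All analyses are descriptive (SAP 6.4), and nothing shows how anaphylaxis frequency would differ by regimen.
- **That the stopping rule flatly contradicts the grading section.** Section 7.4 does assign a scale by event type. What is missing is a statement in 7.8.2 that ties its severity terms to that scale for a reaction that is both allergic and anaphylactic, given that 6.5.1 and Appendices 3 and 4 rank the same signs differently.

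**What to change.** In SAP 10.3, state which anaphylaxis stage counts as grade ≥3. Then show the grade ≥3 TEAE and treatment-related AE tables a second time, with each anaphylactic reaction assigned the worse of its stage and the highest CoFAR grade recorded for its component symptoms. This follows the approach of SAP 10.14 for seriousness and relatedness and the general principle in Protocol 6.5.2. Where no symptom grade is recorded, the stage stands, and a footnote should give the number of such reactions. The prespecified tables and the stage-only summary in 10.14 stay as they are.

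The cost is one extra derivation, two supplementary tables and slightly higher grade ≥3 counts in them. Before programming, confirm on which form component symptoms of non-serious anaphylaxis are graded.

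Separately, Protocol 7.8.2 should be reconciled with 7.4, 6.5.1 and Appendices 3 and 4 on which scale its severe and moderate grades refer to for such a reaction. Which scale should govern is a clinical decision on which no position is taken here.
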